1) Protocol Title

Title: Nexplanon Use in Women Primarily Choosing a Combined Oral Contraceptive: a Proof of Concept Trial

Protocol Version Date: August 12, 2016

2) Objectives

2.1.1 Primary objective:

Evaluate the tolerability (side effects) and acceptability (continuation of the implant throughout the study) of concomitant etonogestrel (ENG) implant use in women choosing a combined oral contraceptive (COC) for contraception.

2.1.2 Secondary objectives:

Evaluate the following outcomes:

- Demonstrate that women desiring a COC are willing to use ENG implant concomitantly as a continuous “back-up” contraceptive
- Bleeding patterns while using a COC concomitantly with ENG implant
- Continuation rate of COC over 6 months of evaluation
- Plan to continue the COC and/or implant after the study

2.1.3 Hypotheses.

1. Women who desire a COC for contraception will be willing to use ENG implant concomitantly as a continuous back-up method.
2. Women using a COC concomitantly with ENG implant will primarily experience regular bleeding patterns, especially after the third cycle of COC use.
3. Tolerability will be good and acceptability high in women who use a COC concomitantly with ENG implant
4. A high percentage of women in the study will still be using the ENG implant after 6 months.

3) Background

[figure not shown]
The ENG implant is a very highly effective method of contraception. The implant is designed to provide contraceptive efficacy for 3 years with a relatively quick return of fertility upon its removal. The implant and the intrauterine device comprise the types of long-acting reversible contraceptive (LARC) methods available throughout the world. Use of these methods is associated with lower rates of unintended pregnancy as compared to shorter acting methods or barrier methods of contraception (Winner 2012).

In the United States, 45% of all pregnancies are unintended (Finer 2016). This latest rate, from 2011, is a drop from a peak of 51.0% in 2008 and lower than the rates of 48.0% in 2001 and 49.2% in 1994 (Henshaw 1998, Finer 2014). This decline is potentially related to increased use of contraception, especially LARC methods

PROTOCOL TITLE: Nexplanon Use in Women Primarily Choosing a Combined Oral Contraceptive: a Proof of Concept Trial

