We anticipate it will take up to 4 months to enroll 20 subjects for this study.

Based on the timeline below, we expect to complete all analyses by September 2017.

STUDY EVENT	MONTHS
Enrollment and 6 month follow-up of subjects	10
Close data set	2
Preparation of final study report and manuscript	3
TOTAL time	15

6) Study Endpoints

As a proof of concept study, the primary outcome is the tolerability (side effects) and acceptability (continuation of ENG implant through 6 months) of concomitant ENG implant use in women choosing a combined oral contraceptive (COC) for contraception. Continuation will be important to assess as some women may choose to discontinue the COC and rely on the ENG implant.

Secondary outcomes will include willingness to accept concomitant ENG implant use with a planned COC, COC continuation rate over 6 months, bleeding patterns and plan to continue ENG implant after 6 months.

All products being used in the study are FDA-approved for contraception. Safety data will be collected in relation to severe adverse outcomes (as defined by the FDA).

7) Procedures Involved

We will recruit women being seen in a UC Davis medical office or who contact our research office. Potential participants must be women currently using COCs or intending to initiate COCs at the time of the office visit.

- “New starters”: subjects who have the implant placed four or less weeks after the initiation of a COC or who are prescribed the COC on the day of the implant initiation.
- “Current pill users” subjects who have been using a COC for more than four weeks prior to implant placement.

PROTOCOL TITLE: Nexplanon Use in Women Primarily Choosing a Combined Oral Contraceptive: a Proof of Concept Trial

We intend to enroll approximately 10 subjects in each of the groups. We expect that most women will be recruited while in the office who decide to initiate COCs or are continuing COC use—these women will be offered the ability to talk to research staff about the study.

Visit 1 (Screening/Enrollment):

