No blood draws will occur during this study.

PROTOCOL TITLE: Nexplanon Use in Women Primarily Choosing a Combined Oral Contraceptive: a Proof of Concept Trial

Data to be collected by study staff include demographics, past medical and gynecologic history, prior and current contraceptive use, and reason for using COC (contraception, medical or both).

Because we are enrolling women who are already currently using COCs or who plan to start COCs, the COC is not a study drug. The study intervention (study drug) is the contraceptive implant. The systemic hormone exposure with a contraceptive implant is minimal relative to a COC. We would not expect any increase in side effects by adding a contraceptive implant to COC users. Of note, the primary risk with COC use is related to the estrogen which can increase the risk of venous thromboembolic disease. The implant has no estrogen. All products being used in the study are FDA-approved for contraception.

8) Data and/or Specimen Management and Confidentiality

All data will be presented descriptively.

The sample is a convenience sample for proof of concept. A total of 20 women will be enrolled to evaluate if women who desire a COC method are willing to accept having a ENG implant placed to use along with their planned COC.

Data that is collected will be kept in a secure and confidential manner in the Department of Obstetrics and Gynecology. Only study staff will have access to both electronic and paper study documents. All study staff will have completed IRB required CITI training and University of California Davis privacy and security trainings, as well as study specific training.

Subjects will be assigned a unique study specific subject number. All data will be associated with that number. No personal identifying information will be used in the data analysis. Study personnel who are delegated by the Principal Investigator will be responsible for the transmission, receipt and management of the data.

At University of California, Davis, the information collected for this study will be recorded on paper source documents. The source documents will be kept in a locked file cabinet in a room with limited access. Only study personnel will have access to both the room with the file cabinet and the file cabinet. This room is locked at all times when study personnel are not occupying the room. Data will be stored at least two years after publication.

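### Willingness to accept the implant is a stated reason for enrolling 20 women, but no count of women offered or declining is planned, so the data can show that some women accept, not what share do

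*Combined protocol and SAP*

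**What the plan says.** Willingness appears in four places in the combined protocol and SAP.

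- Section 2.1.3, Hypothesis 1: "Women who desire a COC for contraception will be willing to use ENG implant concomitantly as a continuous back-up method".
- Section 2.1.2, first secondary objective: "Demonstrate that women desiring a COC are willing to use ENG implant concomitantly as a continuous" back-up method.
- Section 6: "Secondary outcomes will include willingness to accept concomitant ENG implant use with a planned COC". No definition or measure follows.
- Section 8, as the purpose of the sample: "20 women will be enrolled to evaluate if women who desire a COC method are willing to accept having a ENG implant placed". The same section calls this a convenience sample for proof of concept and says that all data will be described.

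On recruitment, Section 7 says that women seen in the office will be offered a talk with research staff, and that women may also contact the research office themselves. Consent comes next, then screening. Eligible women then have the implant placed, at Visit 1 or at an added visit. The user groups are defined by the timing of placement; new starters, for example, include "subjects who have the implant placed four or less weeks after the initiation of a COC". On numbers, "We intend to enroll approximately 10 subjects in each of the groups", and Section 21 provides for storing 20 implant boxes.

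The Section 7 list of data to be collected has no item for women offered, eligible or declining. No other section describes an approach or screening log.

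**The concern.** A woman who does not want the implant leaves before she becomes a subject, either by declining the talk with research staff or by declining after the explanation. Acceptance is therefore a condition of being in the sample, and a description of the enrolled women carries no information about how many refused.

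What is at stake is how the result can be used. The background in Section 3 argues that offering the implant as back-up to pill users could lower unintended pregnancy on a public-health scale. That argument depends on how many women would take up the offer, and the planned data are silent on it. The gap also cannot be repaired later, since refusals that nobody recorded cannot be counted afterwards.

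**Working it through.** **Inputs from the documents.** 20 women in total (Section 8); about 10 per user group (Section 7); up to 4 months to enroll (Section 5); implant placed in eligible women who consent (Section 7). The number of women offered, M, is not given and is assumed below.

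**The plan's own figures.** 10 + 10 = 20 women, and 4 months of enrollment + 6 months of follow-up = the 10 months in the Section 5 table. Both agree. The 20 has no alpha, power, precision or assumed acceptance rate behind it, so there is no sample-size formula to reproduce.

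**Acceptance from the enrolled women alone.** 20/20 = 100%, whatever M is. The nominal exact 95% interval is 83.2% to 100%, but it does not describe willingness, because nobody who refused could enter the denominator.

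**Acceptance if M were known.** The estimate is 20/M. Clopper-Pearson 95% limits are: lower = Beta(0.025; x, M − x + 1), upper = Beta(0.975; x + 1, M − x), with x = 20.

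| Women offered, M (assumed) | 20/M | 95% limits |
|---|---|---|
| 25 | 80% | 59.3% to 93.2% |
| 40 | 50% | 33.8% to 66.2% |
| 100 | 20% | 12.7% to 29.2% |
| 200 | 10% | 6.2% to 15.0% |
| 400 | 5% | 3.1% to 7.6% |

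The planned data would look identical in every row. With a tally, even this small study could tell 50% from 10%.

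**Are the intervals exact here?** Not strictly. Recruitment stops at about 20 enrolled, so M is random and not fixed. Under strict stopping at the 20th acceptor, the lower limit is unchanged and the upper limit becomes Beta(0.975; x, M − x): 65.2% in place of 66.2% for M = 40, and 28.3% in place of 29.2% for M = 100. The Clopper-Pearson interval is slightly wide, which is harmless if it is labelled approximate.

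**Which denominator?** The offer in Section 7 is of a talk about the study, so a woman may decline before she hears of the implant. Suppose 100 are offered the talk, 40 hear the explanation and 20 consent (all assumed). Then 20/40 = 50% of those informed, and 20/100 = 20% of those offered. These answer different questions, so both are needed.

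**The case against.** The strongest reply is that no proportion was ever intended. The title and Section 8 both say proof of concept. Hypothesis 1 and the secondary objective speak of women being willing and state no rate. Where the authors want a proportion they say so: the secondary objectives name a continuation rate for the pill, and Hypothesis 4 reads "A high percentage of women in the study will still be using the ENG implant after 6 months". On that reading, 20 placements answer the question. Much of this stands: the wording leans towards feasibility. It does not settle the matter, because Section 6 lists willingness as an outcome without defining it and Section 8 says that the 20 women evaluate it.

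Two further replies have some force. The Section 7 data list is introduced as what the data include and is not exhaustive (it omits bleeding and adverse events, which are plainly collected), so its silence alone proves little. The firmer ground is that no section at all mentions a log. Research meetings discuss enrollment (Section 10), but that is not a planned count of refusals. And women who consent but have no implant placed would leave a record, yet they had already agreed to join an implant study, so they cannot stand in for those who declined.

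A reader might infer that the trial cannot address Hypothesis 1 at all, that its primary outcome is compromised, or that the authors intend to report 100% acceptance. The documents support none of these. Showing that some women accept is within reach, the primary outcome does not use the missing denominator, and no reporting format for willingness is stated.

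**Conclusion.** The concern holds in a limited form. As planned, the enrolled women give 20/20 by construction. That demonstrates that some pill users or starters accept the implant but cannot show what share do. The size of the gap in this trial is unknown; the 50% to 5% range rests on an assumed 40 to 400 women offered and illustrates the problem without estimating it. The conclusion itself needs no assumption about alpha, power or effect size. It rests only on placement following consent and eligibility, and on the absence of any planned count; a log may be kept in practice, but none is written down.

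Willingness is a secondary outcome and the analysis is descriptive. Tolerability and 6-month implant continuation, the primary outcome, are unaffected. The point should still be fixed, because it touches Hypothesis 1 and the stated purpose of the sample and the remedy is cheap.

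**What to change.** Choose one of two before recruitment starts.

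**Option 1: keep a tally (Sections 7 and 8).** For office-approached women, record de-identified counts of those:

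- offered a talk with research staff;
- declining the talk;
- having the implant and study explained;
- declining after the explanation, with the reason if volunteered;
- consenting;
- having the implant placed.

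Count self-referred women separately, since they have no defined pool of women offered. Report all counts. Report two ratios overall: consented over women to whom the implant was explained, and consented over all women offered. Give each a 95% interval described as approximate because recruitment stops at about 20 enrolled. Show user group only descriptively, where pill use is volunteered: the protocol's groups depend on the placement date, which decliners do not have. State that the ratios also reflect willingness to join a compensated study at no charge.

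**Option 2: restate the aim.** If no tally is kept, reword Hypothesis 1, the secondary objective, the Section 6 outcome and the Section 8 sentence as feasibility of enrolling 20 pill users or starters who accept the implant, and report no acceptance proportion.

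**Cost.** Option 1 is a small recording burden, including for office staff when a woman declines the talk, plus one table. Section 18 limits the research team to self-reported or permitted information, so an IRB clarification may be needed, and the willingness figure may turn out less favourable. Option 2 costs only text.
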